#### CONFIDENTIAL

#### **5.4.1 Use of DataCore/Epic Information for Recruitment Purposes**

Not applicable.

#### **5.5 Duration of Study Participation**

The duration of active study participation is approximately 6 months, with the final follow-up survey with patients occurring 6 months after baseline/enrollment. In cases in which it is difficult to contact or find participants for the follow-up survey, the follow-up visit may be conducted up to 2 months after the 6 month follow-up time period (i.e., up to 8 months after study enrollment). See the [ED-Home Pilot Follow-Up Procedures flow chart](#) in the Study Schema section for details.

#### **5.6 Total Number of Participants and Sites**

We plan to enroll approximately 40 participants at a single site (Bellevue Hospital Center ED). If there are multiple participants who drop out of the study after being consented and/or who cannot be reached for follow-up procedures, we may recruit additional participants as needed to achieve the primary study endpoints.

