### CONFIDENTIAL

## Protocol Summary

[figure not shown]
Title	ED-Home: A pilot feasibility study of a homelessness prevention intervention for substance using emergency department patients
Short Title	ED-Home
Brief Summary	This is a single-arm pilot study to test the feasibility of homelessness prevention and substance use interventions to be delivered to at-risk patients in the Bellevue Hospital emergency department (ED). ED patients (n=40) found eligible for the study will complete a baseline survey and receive referrals to appropriate services, with a final six-month follow-up survey. Interim contacts at 7-10 days, 3 months, and 5 months will be used to assure intervention components were received and to confirm participant contact information. A chart review of participant Bellevue Hospital Center visits will also be performed at the time of the six-month follow-up visit.
Phase	N/A
Objectives	The primary objective is to test the feasibility and acceptability of implementing a homelessness prevention intervention for ED patients with unhealthy alcohol or drug use who are at risk for homelessness.
Methodology	Single-arm pilot feasibility study with pre-post outcome measurement.
Endpoint	Primary endpoints are feasibility of the study and intervention (e.g., participant satisfaction, ability to enroll participants, ability to contact participants at follow-up time points). Exploratory outcomes include 6-month housing and substance use measures.
Study Duration	Approximately 1.5 years.
Participant Duration	Participants will complete a final follow-up survey 6 months after enrollment/baseline visit.
Duration of behavioral intervention	The intervention delivered by investigators will consist of one-time, in-person referrals (at the time of the baseline/enrollment ED visit) and up to 3 follow-up trouble shooting phone calls to occur within 3 months of the initial visit.
Population	Adult ( $\geq 18$ years old), ED patients with unhealthy alcohol or drug use who are not currently homeless but who are predicted to have a high risk of future homelessness. Patients must speak English, reside in NYC, not be critically ill, and not currently be incarcerated. Patients will not be excluded based on race or gender. Projected sample size: approximately n=40.
Study Sites	NYULH and Bellevue Hospital Center Emergency Department
Number of participants	Approximately 40 participants are expected to be enrolled.

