#### **5.7 Participant Withdrawal or Termination**

##### **5.7.1 Reasons for Withdrawal or Termination**

Participants are free to withdraw from participation in the study at any time upon request, which can be made in writing or verbally to the study PI.

Investigators may terminate participation in the study if:

- Any clinical adverse event (AE) or situation occurs such that continued participation in the study would not be in the best interest of the participant.
- It is discovered that participant lacks cognitive or mental capacity to understand the study, whether lacking such capacity at the time of initial consent (unidentified at the time) or during follow-up procedures.

In the case of participant withdrawal or termination, information already collected from the participant will still be used for the purposes of the study unless:

- The study participant explicitly revokes consent to use his/her information for the study, either in writing or verbally to the study PI; or,
- It is determined that the original study consent was not valid (for example, in a case where it is determined that the study participant likely did not have capacity to provide informed consent at the time it was initially conducted).

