##### **5.7.2 Handling of Participant Withdrawals or Termination**

There are no risks to participants from withdrawing from the study or termination of participation. As noted above, participants will be asked if investigators can continue to use information already collected from them for the purposes of the study, including use of their personally identifying information to examine outcomes in data sources specified in the informed consent form (including Department of Homeless Services data and Bellevue Hospital electronic medical record data). No additional information will be collected from participants themselves after withdrawal or termination from the study.

As this is a feasibility study, if fewer than five participants withdraw or are terminated from the study they will not be replaced. If five or more participants withdraw or are terminated from the study, study enrollment may be increased to replace them in order to achieve adequate ability to examine the primary feasibility outcomes.

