***Final Study Visit (6 months, window -2 weeks to +8 weeks)***

- Complete 6 month follow-up survey (see instruments as listed in Section 7.1.1).
- Participant is reminded that this is the final study visit. Participant is thanked for his/her time and has the opportunity to ask any questions about the study.
- Participant given \$50 (cash or gift-card) follow-up reimbursement.

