## **10.5 Sample Size**

Our goal is to test the feasibility and acceptability of the intervention and study processes. We expect this goal can be accomplished by enrolling approximately 40 ED patients, which will allow us to try the intervention for a range of different types of patients and to encounter a wide array of issues to be considered for a future large trial. The enrollment goal of approximately 40 patients, which equates to 1–2 patients per week over 6 months, is feasible. As this is a feasibility study only—not a study meant to test outcome effects—further sample size calculations are unnecessary and would be inappropriate.

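### Do the two rules for adding participants after dropout (5.6 and 5.7.2) conflict enough, or overrun the calendar enough, to need a change?

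*Combined protocol and SAP*

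**What the plan says.** Section 5.6 plans about 40 participants at one site. If there are "multiple participants who drop out of the study after being consented and/or who cannot be reached for follow-up procedures, we may recruit" further people as needed, with the stated aim of achieving the primary endpoints. It gives no number for how many dropouts trigger this, and it does not say at which contact a participant counts as unreachable.

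Section 5.7.2 gives a number: "if fewer than five participants withdraw or are terminated from the study they will not be replaced". At five or more, enrolment may be increased. It covers withdrawal and termination and is silent on non-contact.

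Four places set the calendar:
- Section 10.5 plans 1-2 "patients per week over 6 months, is feasible".
- Section 5.5 allows the final survey of a hard-to-find participant "up to 8 months after study enrollment".
- Section 7.3.4 gives the final visit a "window -2 weeks to +8 weeks".
- The Protocol Summary gives the study duration as "Approximately 1.5 years".

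On data use after withdrawal, 5.7.2 writes "As noted above, participants will be asked if investigators can continue to use information already collected from them". Section 5.7.1, to which this points back, has no asking step; its default is that "information already collected from the participant will still be used for the purposes of the study unless" consent is revoked or proves to have been invalid.

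**The concern.** Read literally, a team with two to four withdrawals finds one section that lets it recruit and another that says it will not. That is an ordinary number of withdrawals in a group of 40.

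The non-contact trigger raises a second doubt. Contact at follow-up is itself a primary feasibility endpoint (10.4.2), so the outcome can drive enrolment. An unreached participant has also already supplied the contact result. If non-contact is accepted only when the window closes, the added person starts late and needs another 5.5 to 8 months. The study would then run past its stated length, or the added people would have no 6-month survey.

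Two smaller points sit beside these. The back-reference in 5.7.2 leads nowhere, and 10.4.2 names no denominator for retention, although it does name one for eligibility and for agreement to participate. A retention rate computed on a shifting base would mislead the planners of the larger trial that this pilot is meant to inform.

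**Working it through.** **The plan's own figures.** Six months is about 26 weeks. At 1-2 per week that gives 26 to 52 participants, and 40/26 = 1.54 per week, so the target of 40 fits. Without additions, the last final visit falls at 6 + 6 = month 12 to 6 + 8 = month 14, which leaves 4 to 6 months of the 18.

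**The threshold.**

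| Withdrawn or terminated | 5.6 | 5.7.2 |
|---|---|---|
| 0-1 | no addition | not replaced |
| 2-4 | may add | not replaced |
| 5 or more | may add | may add |

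The sections differ in the middle row only. The documents give no withdrawal rate. For assumed rates of 2%, 5%, 10%, 15% and 20%, the binomial probability of two to four withdrawals among 40 is 0.19, 0.55, 0.55, 0.25 and 0.07. The situation is therefore plausible, but its effect is enrolment of 40, or 42 to 44 with one-for-one additions. For a proportion of 75% (assumed), the approximate 95% half-width is 1.96 × √(0.75 × 0.25/40) = 13.4 points with 40 participants and 1.96 × √(0.75 × 0.25/44) = 12.8 points with 44. The difference of 0.6 points changes no descriptive conclusion.

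**The calendar.** Assume that month 0 is first enrolment, accrual is even over 6 months, and the addition is recruited at once. For the last participant enrolled, the addition's final visit falls at 6 + (months until non-contact is judged) + (6 to 8 months of follow-up):

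| Non-contact judged at | Addition's final visit (month) |
|---|---|
| Day 7-10 (about 0.33 months) | 12.3 to 14.3 |
| 3 months | 15 to 17 |
| 5 months | 17 to 19 |
| 6 months | 18 to 20 |
| 8 months (window closes) | 20 to 22 (19.5 if seen two weeks early) |

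If the judgement waits for window close, an addition fits within 18 months only for originals enrolled by month 18 − 8 − 5.5 = 4.5, 18 − 8 − 6 = 4, or 18 − 8 − 8 = 2. By those months 40 × 4.5/6 = 30, 40 × 4/6 = 26.7 and 40 × 2/6 = 13.3 people are enrolled, so about 10, 13 or 27 of 40 would not be covered. The overrun is thus real for late judgement and absent for early judgement.

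**The denominator.** Section 10.3 specifies a single dataset holding all participants. Suppose 30 of 40 are reached and 10 additions are reached at the same 75%. Counting everyone gives (30 + 7.5)/50 = 75.0%. Substituting the additions for the unreached would give 37.5/40 = 93.8%, but 10.3 does not provide for substitution. Letting non-contact drive enrolment adds almost no bias when everyone is counted: averaging (X + 0.75 × (40 − X))/(80 − X) over X ~ Binomial(40, 0.75) gives 75.3%, or 0.3 points above the true 75%. The exact 95% interval for 30/40 is 58.8% to 87.3%.

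What remains is people whose data are removed because consent was revoked or invalid. If they also left the headcount, one to four of them would move 30/40 = 75.0% to 30/39 = 76.9%, 30/38 = 78.9%, 30/37 = 81.1% or 30/36 = 83.3%. All lie inside that interval.

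**The case for a change.** The strongest case for a change is that it is cheap. The conflict for two to four withdrawals is literal; 5.6 does not say that its unquantified trigger means five or more, and dropping out is nowhere distinguished from withdrawing. Section 14.3 treats any noncompliance with the protocol as a deviation, so staff acting on 5.6 could be said to depart from 5.7.2. No passage available to us gives a cap on additions, a recruitment cut-off or a time for declaring non-contact. The calendar is also tighter if accrual is slow: at 1 per week, 40 participants take about 9.2 months, and an addition judged at 3 months would finish at month 18.2 to 20.2. A few words and an IRB amendment would settle all this.

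Part of it stands. The wording does differ, and late judgement of non-contact does overrun. But 5.6 only permits and 5.7.2 only restricts, so following the second satisfies both, and its number can be read as giving content to the first. The investigators also keep the discretion not to add anyone late. Follow-up contacts begin at day 7-10, so 5.6 need not be read as waiting for the final visit. Sections 5.5 and 7.3.4 refer to a follow-up flow chart for hard-to-find participants and missed visits; that figure is not reproduced in the text available here and may settle the timing. The duration is approximate and has no stated start point.

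Removing the non-contact trigger would carry a cost. With 10 of 40 unreached, 10 × 0.75 = 7.5, so about 7 or 8 further 6-month surveys on satisfaction and service receipt would be lost. Those are primary endpoints too, and 6.1.3 relies mainly on self-report for service receipt. An addition who never reaches the 6-month visit still contributes to the consent, referral and immediate-satisfaction measures.

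**Conclusion.** The mismatch between 5.6 and 5.7.2 is real but has no consequence for the results. It concerns 40 versus 42 to 44 participants in a single-arm descriptive pilot whose target is approximate, and the stricter section can be followed without breaching the other. The overrun is one scenario, not a property of the plan: on the planned 6-month accrual it requires non-contact to be judged at about the 5-month contact or later, and its worst case of month 22 requires judgement at window close followed by a full-window visit. The non-contact trigger is a fair trade-off between time and extra follow-up data. Section 10.3 largely answers the denominator question, provided analysts count additions in addition to the original participants and report how many people had data removed. The back-reference in 5.7.2 is a clerical slip. The conclusion rests on the calendar assumptions stated above, on an illustrative 75% contact rate, and on text that lacks the flow chart. If the protocol is amended for another reason, pointing 5.6 to the threshold in 5.7.2 and naming the contact at which non-contact is judged would be sensible housekeeping.

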#### **5.7 Participant Withdrawal or Termination**

##### **5.7.1 Reasons for Withdrawal or Termination**

Participants are free to withdraw from participation in the study at any time upon request, which can be made in writing or verbally to the study PI.

Investigators may terminate participation in the study if:

- Any clinical adverse event (AE) or situation occurs such that continued participation in the study would not be in the best interest of the participant.
- It is discovered that participant lacks cognitive or mental capacity to understand the study, whether lacking such capacity at the time of initial consent (unidentified at the time) or during follow-up procedures.

In the case of participant withdrawal or termination, information already collected from the participant will still be used for the purposes of the study unless:

- The study participant explicitly revokes consent to use his/her information for the study, either in writing or verbally to the study PI; or,
- It is determined that the original study consent was not valid (for example, in a case where it is determined that the study participant likely did not have capacity to provide informed consent at the time it was initially conducted).

##### **5.7.2 Handling of Participant Withdrawals or Termination**

There are no risks to participants from withdrawing from the study or termination of participation. As noted above, participants will be asked if investigators can continue to use information already collected from them for the purposes of the study, including use of their personally identifying information to examine outcomes in data sources specified in the informed consent form (including Department of Homeless Services data and Bellevue Hospital electronic medical record data). No additional information will be collected from participants themselves after withdrawal or termination from the study.

As this is a feasibility study, if fewer than five participants withdraw or are terminated from the study they will not be replaced. If five or more participants withdraw or are terminated from the study, study enrollment may be increased to replace them in order to achieve adequate ability to examine the primary feasibility outcomes.

##### **5.7.3 Premature Termination or Suspension of Study**

Premature termination or suspension of the study is not expected.

#### CONFIDENTIAL

This study may be temporarily suspended or prematurely terminated if there is sufficient reasonable cause. If the study is prematurely terminated or suspended, the PI will promptly inform the IRB and the study sponsor, and will provide the reason(s) for the termination or suspension.

Circumstances that may warrant termination or suspension include, but are not limited to:

- Determination of unexpected, significant, or unacceptable risk to participants
- Insufficient compliance to protocol requirements
- Data that are not sufficiently complete and/or evaluable
- Lack of adequate funding to complete the study

None of the above are expected to occur for this small feasibility pilot study.

The study may resume once concerns about safety, protocol compliance, and/or data quality are addressed and satisfy the sponsor and/or IRB.

## 6 Behavioral/Social Intervention

### 6.1 Study Behavioral or Social Intervention(s) Description

The intervention will consist of:

- 1) Referral to Homebase homelessness prevention services offered by community-based organizations in NYC;
- 2) Referral to substance use services (SBIRT and Addiction Leads) available at Bellevue Hospital;
- 3) Follow-up to ensure participants receive needed services.

Each of these components is described in more detail below.

#### Referral to Homebase homelessness prevention services

Homebase is the homelessness prevention program offered by the NYC Department of Social Services. It has been found in prior research to be effective in reducing future shelter entries among New Yorkers at risk for homelessness. Homebase services are tailored to individual needs and may include assistance with landlord-tenant mediation, assistance in paying rental arrears, other financial assistance, assistance with benefits applications (e.g., SNAP), family mediation, and other services. Upon initial arrival to a Homebase office, clients are assessed for Homebase service eligibility by a case worker. Eligible clients are assigned to a case worker and receive services. Homebase services are currently provided by seven different community based organizations in NYC, at more than fifteen different locations spread throughout the city; the specific location at which clients will be served depends on their zip code.

Study staff will determine to which Homebase office to refer study participants based on their zip code. Study staff will write down the name, location, hours, and contact information for the appropriate Homebase office and give this information to participants. Study staff will also provide study participants with an informational handout on Homebase (see *ED-Home Homebase Information Sheet* attachment). Study staff will make the referral to Homebase using an *ED-Home Homebase Referral Form for Bellevue Pilot* which will be e-mailed to the appropriate Homebase office as well as to related staff from the NYC Department of Social Services (see *ED-Home Email Template for Homebase*). This referral form was developed in conjunction with a pilot program of the Department of Health and Mental Hygiene of hospital referrals to Homebase in NYC. The Homebase providers are asked to reply to study staff by e-mail within 1 week to confirm that the referral was received and appropriate, contact the participant within 1 week either by phone or NYULH SendSafe email to discuss with the participant how to prepare for visit to Homebase and schedule an appointment, and reply to study staff by e-mail within 6 weeks to confirm whether the client was enrolled, declined to enroll, or was unable to be enrolled in Homebase services. Additionally, study staff may communicate with Homebase staff and/or the NYC Department of Social Services (including Human Resources Administration Prevention & Community Services) by phone and/or NYULH SendSafe email to facilitate if the participant has not been in contact with Homebase since baseline or to ensure referrals are successful. A successful referral would mean that the participant went to Homebase and spoke with someone there about obtaining needed services.

### Referral to substance use services

Bellevue Hospital Center already offers SBIRT (Screening, Brief Intervention, and Referral to Treatment) services for emergency department patients. These services are free of charge and are available to all patients during times when SBIRT staff are present. SBIRT services have been described in the prior literature. In brief, they consist of assessing patients' substance use, offering a brief intervention using principles of harm reduction and motivational interviewing, and referring patients to substance use treatment as appropriate. By its nature, these services are tailored based on individual needs. Participants may be provided with brochures or other written material about substance use as appropriate for the individual. All SBIRT providers have been trained in SBIRT procedures. SBIRT is provided as part of routine ED care, separate from this study.

The Bellevue Hospital Center ED also offers new substance use services called Addiction Leads, which consists of a peer counselor/social worker team. These services are also free of charge and are available to patients who need them during the hours in which the peer counselor/social worker are available. This is a new program at Bellevue Hospital. As such, the exact services that will be provided may vary somewhat during the study time period but will consist of assessing patients' substance use, counseling patients about their substance use, connecting patients with medication therapy for substance use as appropriate (including via prescriptions given by ED physicians), and connecting patients with outpatient or inpatient substance use treatment referrals as appropriate. Patients may be provided with brochures or other written material about substance use as appropriate for the individual.

The role of the study staff will be to contact the SBIRT and/or Addiction Leads teams during the participant's baseline ED visit. The SBIRT and/or Addiction Leads teams will then assess and provide services to the participant during the baseline ED visit. The exact services provided will depend on participant needs, as these are designed to be individually tailored services. Of note, both of these programs are considered to be standard of care in the ED; study staff will simply facilitate by making the referral and ensuring participants receive services during their ED visit. Participants will be referred to one or both of these substance use services depending on availability of service staff, participant need, and participant interest.

